Recording of AEs		X	X	X	X	X	X	X	X	X	X	X	X
Blood sampling for PK ⁿ		X		X								X	
Blood sampling for ADA		X		X				X ^o				X	X
Blood sampling for IgG and IgG subclasses ^p		X	X	X		X		X		X		X	X
Blood sampling for IgA, IgM, IgE		X						X ^q				X ^r	X
Blood sampling for exploratory safety biomarker analysis ^s			X										
MG-specific autoantibodies		X		X				X ^o				X	X
Serum complement levels (C3,C4) and cytokines ^t			X					X					
Plasma complement levels (C3a and C5a) ^t			X					X					

Table 1-1: Schedule of activities

	Week	Weeks 1-4		Weeks 5-8				Weeks 9-48 ^a		Weeks 49-51		Week 52	Week 60
	Visit ^b	1 (Screening /Baseline) ^c	2-4	5	6	7	8	1 st visit	2 nd , 3 rd , and 4 th visits	49	50 51	52 or PEOT	53 EOS
Assessments	Visit type	S	S	S	H	S	H	S	H	S	H	S	S

ADA=anti-drug antibody; ADL=activities of daily living; AE=adverse event; AESM=adverse events of special monitoring; C-SSRS= Columbia Suicide Severity Rating Scale; ECG=electrocardiogram; EOS=End of Study; EQ-5D-5L=5-level European quality of life 5 dimension; GI=gastrointestinal; H=home visit; HIV=human immunodeficiency virus; Ig=immunoglobulin; IGRA=interferon gamma release assay; IMP=investigational medicinal product; INR=international normalized ratio; IRT=interactive response technology; MG=myasthenia gravis; MGII=myasthenia gravis impairment index; MG-ADL=myasthenia gravis-activities of daily living; MGFA=Myasthenia Gravis Foundation of America; MGQoL15r=revised 15-item myasthenia gravis quality of life questionnaire; PEOT=premature end of treatment; PK=pharmacokinetic(s); PRO=patient-reported outcome; PTT=partial thromboplastin time; QMG=quantitative myasthenia gravis test; S=site visit

^a From Weeks 9 to 48, the schedule will operate on recurring 4-week cycles wherein the first visit of each 4 weeks will be site visits and the subsequent 3 visits (2nd, 3rd, and 4th visits) will be home visits. Accordingly, Visits 9, 13, 17, 21, 25, 29, 33, 37, 41, and 45 will be site visits and the remaining visits will be home visits. At the discretion of the Investigator, home visits may be changed to site visits. Study participants may also choose to complete the visits at the site on the scheduled home visits.

^b Visit windows of ±2 days are allowed for all visits.

^c For any study participant who enrolls in MG0004, the final visit in MG0003 (Visit 14) or MGC003 (Visit 14) will serve as Visit 1 in MG0004. All activities should be completed at Visit 1 (±1 week).

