^d For criteria pertaining to laboratory measures, the last available value from MG0003 or MGC003 will be used for evaluation of study participant eligibility, as long as the measurement was taken within the last 4 weeks (not older than 32 days) prior to MG0004 screening.

^e To be collected four times during the study: Screening/Baseline, 1 Week 25 (site visit), Week 52 (or PEOT), and EOS Visit.

^f A full Columbia-Suicide Severity Rating Scale (C-SSRS) assessment will be performed only when study participant has a positive response to Question 1 of the suicidal ideation query. If a study participant has active suicidal ideation as confirmed by the answer “Yes” to Question 4 or Question 5 of the C-SSRS assessments, the study participant will be excluded or withdrawn from the study and immediately referred to a mental healthcare professional. Complete C-SSRS will observe the “since last visit” version recorded at Visit 14 in MG0003 or MGC003.

^g MGII is optional for all study participants.

^h From Weeks 9 to 48, an ECG will be performed every 3 months (ie, Weeks 9, 21, 33, and 45).

ⁱ Urine pregnancy test will be performed using a dipstick test; a positive urine pregnancy test must be confirmed using a serum pregnancy test.

^j Every 6 months.

^k From Weeks 9 to 48, the tuberculosis questionnaire will be performed every 3 months (ie, Weeks 9, 21, 33, and 45).

- ^l Study participants must be observed at site postdose for at least 4 hours following the first 2 infusions, and then 2 hours thereafter for subsequent infusions until Week 7, where the participant can be observed for 1 hour at the Investigator's discretion.
- ^m No IMP administration will occur during the PEOT visit for study participants who withdraw from the study or discontinue IMP.
- ⁿ PK samples should be taken predose for all study participants.
- ^o From Weeks 9 to 48, ADA- and MG-specific autoantibodies will be measured every 3 months (ie, Weeks 9, 21, 33, and 45).
- ^p Total IgG will be assessed at all scheduled onsite visits; IgG subclasses will be assessed at Visit 1 and every 3 months thereafter.
- ^q From Weeks 9 to 48, blood sampling for IgA, IgE and IgM will be measured every 3 months (ie, Weeks 9, 21, 33, and 45).
- ^r To be performed only in the event of a PEOT Visit.

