Individual study participants will be assessed for ADA participant status, composed of 6 categories: ADA negative, inconclusive, and ADA positive, whereby a positive participant’s status is determined as originating from a treatment-induced, boosted, reduced or unaffected ADA response.

Study participants who are identified as being treatment-induced or treatment-boosted ADA-positive will be grouped as treatment-emergent (TE)-ADA positive participants. Study participants who are identified as being treatment-reduced or treatment-unaffected ADA-positive will be grouped as non-TE-ADA positive participants. Both TE-ADA positive and non-TE-ADA positive participants will be further classified as NAb negative or NAb positive.

The individual and combined ADA participant categories will be derived and summarized through each of the scheduled sampling points (ie Week 5, 9, 21, 33, 45, 52 and 60) and EOS visit, unless specified otherwise.

Table 10-1: Terms and Definitions for ADA Status Evaluation in Study Participant

Classification	Classification Label	Definition
Individual participant categories		
1	Pre-ADA negative – treatment induced ADA negative (ADA-NEG)	Study participants who have an ADA negative sample at Baseline and at all sampling points post-Baseline up to the timepoint of interest.
2	Inconclusive	Study participants who have an ADA positive or negative Baseline sample and some post-Baseline samples are missing or inconclusive, while other post-Baseline samples are ADA negative up to the timepoint of interest.
3	Pre-ADA negative – treatment induced ADA positive (TI-POS)	Study participants who have an ADA negative sample at Baseline and have at least one ADA positive sample at any sampling point post-Baseline up to the timepoint of interest.
4	Pre-ADA positive – treatment boosted ADA positive (TB-POS)	Study participants who have an ADA positive sample at Baseline and at least one ADA positive sample at any sampling point post-Baseline up to the timepoint of interest, with increased titer values compared to Baseline (greater than a predefined fold difference increase from Baseline value which will be defined within the validation of the assay i.e. MSR of the assay).

5	Pre-ADA positive – treatment reduced ADA positive (TR-POS)	Study participants with an ADA positive sample at Baseline, and ADA negative samples at all sampling points post-Baseline up to the timepoint of interest.

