6	Pre-ADA positive – treatment unaffected ADA positive (TU-POS)	Study participants with an ADA positive sample at Baseline and an ADA positive sample at any sampling point post-Baseline up to the timepoint of interest, with titer values of the same magnitude as Baseline (less than a predefined fold difference from the Baseline value which will be defined within the validation of the assay, i.e. MSR of the assay ¹).
Combined participant categories		
7	Treatment emergent ADA positive (TE-POS)	Includes study participants who are treatment induced ADA positive (category 3) or treatment boosted ADA positive (category 4).
8	Non-treatment emergent ADA positive (Non-TE-POS)	Includes study participants who are treatment reduced ADA positive (category 5) or treatment unaffected ADA positive (category 6).
9	Treatment emergent ADA positive – NAb positive (TE-POS, NAb-POS)	Includes study participants who are treatment emergent positive (category 7) and have at least one NAb positive sample.
10	Treatment emergent ADA positive – NAb negative (TE-POS, NAb-NEG)	Includes study participants who are treatment emergent positive (category 7) and have no NAb positive samples.
11	Non-treatment emergent ADA positive - NAb positive (Non-TE-POS, NAb-POS)	Includes study participants who are non-treatment emergent positive (category 8) and have at least one NAb positive sample.
12	Non-treatment emergent ADA positive - NAb negative (Non-TE-POS, NAb-NEG)	Includes study participants who are non-treatment emergent positive (category 8) and have no NAb positive samples.
¹ The fold difference increase from baseline value, i.e. the minimum significant ratio (MSR=1.36) determined during assay validation, will be reported in the relevant tables, listings and figures. It reflects the fold difference in titer level that considered higher than the assay variation in titer determination.		

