- Individual time course plots for ADA positive study participants with at least one ADA positive sample, representing ADA and NAb titers (on log-scale), percentage CFB for total IgG and MG-specific autoantibodies, and CFB for MG-ADL total score. The sub-title of the graph will include the study participant number, bodyweight category, treatment group (including prior treatment group in MG0003), and individual ADA participant category (3, 4, 5, 6) up to EOS. The dosing will be represented in the x-axis with bars/arrows at the time of dose.
- Spaghetti plots of individual time course of ADA titer for ADA positive participants in categories 9, 10, 11 and 12 (determined through EOS), whereby all categories are overlaid on the same plot and visualized using different symbols and colors. The ADA titer results will be presented on a log-scale. Dosing time points should be indicated below the x-axis. The same plot will be repeated for NAb titer for NAb positive participants in categories 9 and 11.
- A box-and-whisker plot of maximum postdose ADA titer (on log-scale) through Week 5, Week 9, Week 52 and EOS versus ADA participant category for categories 9, 10, 11 and 12 (determined for the corresponding time period of interest). The same plot will be repeated for NAb titer for ADA participant categories 9 and 11.
- Time course plot of mean CFB in MG-ADL total score, summarized by ADA participant category 1, 2, 9, 10, 11 and 12. Categories will be determined for the time period from baseline up to timepoint of interest (Week 5, 9, 52 and EOS). Separate plots for each treatment group and RLZ total [REDACTED].

- Spaghetti plots of individual time course of percentage CFB for total IgG, for each of the ADA participant categories 1, 2, 9, 10, 11 and 12 and time period of interest (Baseline up to Week 5, Week 9, and EOS) whereby the ADA participant categories are multipaneled. Separate plots for each treatment group and RLZ total [REDACTED]. Individual samples that tested positive for ADA will be visualized using a symbol and/or color. Dosing time points should be indicated below the x-axis.
- Scatter dot plot of individual CFB in MG-ADL total score categorized by ADA titer tertile (including category ADA not present) for each scheduled assessment (Week 5, 9, 21, 33, 45, 52, and 60). The same plot will be repeated for NAb titer.

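### As worded, the ADA categories in SAP Table 10-1 leave some participants unclassified at Week 5 and can count a boosted participant as both treatment-emergent and non-treatment-emergent

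*SAP*

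**What the plan says.** SAP 10.3.1 gives each participant an ADA status drawn from six individual categories, accumulated over time: "The individual and combined ADA participant categories will be derived and summarized through each of the scheduled sampling points (ie Week 5, 9, 21, 33," then Weeks 45, 52 and 60.

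The definitions in Table 10-1 that matter here are:

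- Category 1 (ADA negative): "ADA negative sample at Baseline and at all sampling points post-Baseline up to the timepoint of interest".
- Category 2 (Inconclusive): a positive or negative Baseline sample, where "some post-Baseline samples are missing or inconclusive, while other post-Baseline samples are ADA negative up to the timepoint of interest".
- Category 4 (treatment boosted): positive at Baseline, with "at least one ADA positive sample at any sampling point post-Baseline up to the timepoint of interest, with increased titer values compared to Baseline" by more than the MSR.
- Category 6 (treatment unaffected): positive at Baseline, with "an ADA positive sample at any sampling point post-Baseline up to the timepoint of interest, with titer values of the same magnitude as Baseline", that is, within the MSR.

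The table's footnote sets the MSR at 1.36. Category 4 feeds category 7 (TE-POS) and category 6 feeds category 8 (Non-TE-POS). These are then split by neutralizing antibody into 9 or 10 and 11 or 12.

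SAP 10.3.2 tabulates every category at each scheduled visit. It also plots MG-ADL change by categories 1, 2 and 9 to 12, with this instruction: "Categories will be determined for the time period from baseline up to timepoint of interest (Week 5, 9, 52 and EOS"). The individual IgG plots use the same categories for Baseline to Week 5, Week 9 and EOS. The TEAE tables, and the table of hypersensitivity, anaphylactic and infusion reactions, use categories 1, 2, 7 and 8 at Week 9 and EOS.

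**The concern.** A status variable of this kind should give every evaluable participant exactly one value at each timepoint. Table 10-1 fails in two ways.

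First, category 2 asks for a missing or inconclusive sample together with a different, negative one. With one scheduled sample by Week 5 it must be empty then. The people it is meant to hold fit nowhere else.

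Second, category 6 is met by a suitable sample at any one timepoint, and nothing says that category 4 takes priority. One person can then satisfy both and appear in the treatment-emergent and the non-treatment-emergent columns of the same safety table, which blurs the comparison that the table is for. Unless the text is settled, the programmer must choose a rule while open-label data are already visible.

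**Working it through.** **Inputs**

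- Scheduled ADA samples, Protocol Table 1-1, row "Blood sampling for ADA": Visit 1, Visit 5, first visits of the 4-week cycles, Visit 52 or PEOT, and EOS (Week 60). The footnote limits the cycle visits: "ADA- and MG-specific autoantibodies will be measured every 3 months (ie, Weeks 9, 21, 33, and 45").
- Post-Baseline points are therefore 5; 9, 21, 33, 45; 52; 60, which is 7. This reproduces the SAP list.
- SAP 10.3.1 does not count MG0003 post-baseline samples towards MG0004 status, so they cannot supply a second sample by Week 5.
- SAP 10.3 drops only participants with no evaluable post-baseline sample at all. Someone with an unusable Week 5 sample and a usable later one stays in.
- Maximum sample size: 240 (SAP 3.9).

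**Step 1: Week 5, one sample.** Code a sample as N (negative), M (missing or inconclusive) or P (positive). For Baseline-positive participants, split P into B (above 1.36 times Baseline), U (within the MSR) and D (positive but lower).

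- Baseline negative: N gives category 1, P gives category 3, M gives none.
- Baseline positive: N gives category 5, B gives category 4, U or D gives category 6, M gives none.

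Category 2 fits 0 of 3 and 0 of 5 patterns. D is read here as category 6; if the MSR were applied in both directions, D alone would have no category either.

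**Step 2: later timepoints.** All patterns were enumerated for k samples. In each Baseline group exactly one pattern has no category at every timepoint: all samples so far are M. For Baseline-positive participants, patterns with at least one B number 5^k − 4^k. Those that also contain a U or D number 5^k − 4^k − 3^k + 2^k.

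| Through | k | Patterns with a boosted sample | Also category 6 |
|---|---|---|---|
| Week 5 | 1 | 5 − 4 = 1 | 5 − 4 − 3 + 2 = 0 |
| Week 9 | 2 | 25 − 16 = 9 | 25 − 16 − 9 + 4 = 4 |
| Week 21 | 3 | 125 − 64 = 61 | 125 − 64 − 27 + 8 = 42 |

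Overlap is impossible at Week 5 and possible from Week 9. These are counts of patterns, not probabilities.

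**Step 3: size of the gap.** The documents give no rate of unusable Week 5 samples. For assumed rates of 2%, 5%, 10% and 20%, 240 × rate = 4.8, 12, 24 and 48. These are upper bounds: 240 is a maximum, and anyone with no later evaluable sample is excluded anyway.

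**Step 4: size of the overlap.** The documents give neither a pre-existing ADA rate nor a titre course. Suppose all k samples are positive and each is independently boosted with probability q. The share of boosted participants who also meet category 6 is [1 − (1−q)^k − q^k] / [1 − (1−q)^k].

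- k = 1: 0%.
- k = 2: q = 0.1 gives 0.18/0.19 = 95%; q = 0.5 gives 0.50/0.75 = 67%; q = 0.9 gives 0.18/0.99 = 18%.
- k = 7: q = 0.1, 0.5, 0.9 and 0.95 give about 100%, 99%, 52% and 30%.

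If the boost instead persists once begun, with onset probability h at each visit, the share is 1 − h/[1 − (1−h)^k]. For k = 7 and h = 0.3, 0.5, 0.7 and 0.9 this is 67%, 50%, 30% and 10%. If every positive sample is boosted, it is 0%. The answer runs from 0% to about 100% and is set by the assumption.

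**The case against.** The case for leaving the table alone has four parts.

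- **Intent.** The SAP means each participant to have one status, and someone with a boosted titre is not naturally called unaffected. A programmer building a single-valued variable would probably let category 4 win. That is a fair guess about practice, but it does not settle the text: categories 1 and 5 require all sampling points where category 6 accepts any, and no precedence is stated.
- **Nobody vanishes at Week 5.** The by-visit sample-status table shows missing and inconclusive results separately. Under SAP 3.1, percentages are based on observed data with the denominator shown. A participant who missed Visit 5 also has no Week 5 IgG or MG-ADL value to plot. All of this limits the harm. It does not explain why the Week 5 figures ask for a category that scheduled samples cannot fill.
- **Inconclusive results may be rare.** They require drug concentrations above 200 µg/mL, and PK samples are taken predose. That leaves mainly missing samples, which SAP 4.2.3 does expect because of COVID-19.
- **Little room for double counting.** The safety tables by category are specified only at Week 9 and EOS, and at Week 9 the two samples would have to disagree. Participants can leave for MG0007 after six visits, so many may have few samples. For those given rozanolixizumab in MG0003, Baseline is the MG0003 value, so a boost may already be present at Week 5 and persist.

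A reader might infer that most boosted participants would be double counted, or that an unchanged sample followed by a boosted one is the usual course. The documents do not support this. They contain no titre data, and any percentage restates the onset and duration assumed for the boost.

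**Conclusion.** Both defects follow from the wording of Table 10-1. On scheduled samples, category 2 cannot be met through Week 5. A participant with an unusable Week 5 sample and a later evaluable one has no Week 5 category. After that, only participants whose every sample so far is missing or inconclusive are left out. From Week 9, categories 4 and 6 can both apply to one Baseline-positive participant, who can then be counted in categories 7 and 8, including in the TEAE and hypersensitivity tables.

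The number affected is unknown and probably small. The overlap concerns only participants who are positive at Baseline and boosted. The outputs are descriptive, and ADA is neither a primary nor a secondary objective. The point is minor: the rules are wrong as written, with limited consequence.

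The conclusion assumes scheduled sampling. An unscheduled draw, which Protocol 8.6 allows, could occasionally give a second sample by Week 5. It also assumes that the evaluability rule in SAP 10.3 applies to the whole study, as worded. Applied at each timepoint, it would exclude the Week 5 cases instead of leaving them unclassified.

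**What to change.** Reword two rows of Table 10-1:

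- *Category 2:* Baseline sample ADA positive or negative; no positive sample after Baseline; one or more post-Baseline samples missing or inconclusive, through the timepoint considered.
- *Category 6:* Baseline sample ADA positive; one or more positive samples after Baseline; none with a titre exceeding Baseline by more than the MSR, through the timepoint considered. Category 4 therefore takes precedence.

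Re-running the enumeration with these definitions gives 0 patterns without a category and 0 with two, at all seven timepoints. An unusable Week 5 sample then falls in category 2, so the Week 5 outputs can be produced as requested. The cost is two table entries and the matching program logic, with no new data, visits or assays.

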9.3.3.3 Anti-drug antibody analyses

A tiered ADA approach will be used for the study. Anti-drug antibody assessments will involve screening (above or below the cutpoint) of all samples for ADA, followed by a confirmatory assessment (confirmed or not confirmed positive) leading to an anti-rozanolixizumab antibody positive or negative assessment for each sample and a subsequent titration of those anti-rozanolixizumab antibody-positive samples during treatment and observation periods. For anti-rozanolixizumab antibody-positive samples (or subset of) further characterization for neutralizing ADA potential in vitro will be performed.

All immunogenicity analyses will be based on the SS (Section 9.1).

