10.3 Anti-drug antibody and neutralizing antibody (NAb) status

For the immunogenicity assessment, two types of anti-drug antibody (ADA) assays will be performed, a binding anti-drug antibody assay and a neutralizing antibody assay.

For the binding assay, the ADA of rozanolixizumab will be measured using a three-tiered assay approach: screening assay, confirmatory assay and titration assay. Any sample confirmed positive for the binding ADA assay will be tested in the neutralizing assay, which produces a positive or negative result.

Evaluation of rozanolixizumab immunogenicity will be performed using data from all evaluable study participants in the SS, defined as all study participants who have an evaluable pretreatment (baseline) sample (negative or positive ADA sample status), and at least 1 evaluable post-baseline value.

Study participants with an evaluable pretreatment (baseline) sample but without a single evaluable sample taken post-baseline will be included in the reporting of pre-existing ADA but excluded from all other immunogenicity analyses.

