10.3.1 Data consideration

ADA Sample Status

The ADA sample status will be determined for each pre-treatment (Baseline) and post-treatment (post-Baseline) visit where samples are taken for ADA analysis.

- Sample values that are either 'negative screen' or 'positive screen' and 'negative immunodepletion' will be defined as **ADA negative** if corresponding rozanolixizumab concentrations are equal or below the validated drug tolerance limit of the ADA assay (200µg/mL rozanolixizumab) allowing detection of 100ng/mL ADA
- Sample values that are either 'negative screen' or the combination of 'positive screen' and 'negative immuno-depletion', but with corresponding rozanolixizumab concentrations above the validated drug tolerance limit of the ADA assay, will be defined as **ADA inconclusive**
- Sample values that are 'positive screen' and 'positive immunodepletion' will be defined as **ADA positive**
- Samples that could not be tested for ADA status due to inadequate sample volume, mishandling, or errors in sample collection, processing, storage, etc., will be defined as **Missing**.

Note: if a participant has no baseline ADA, then she/he can't be treated as "Inconclusive".

Neutralizing antibody (NAb) sample status (positive/negative/missing) will be determined for ADA positive samples. Samples that are NAb positive will be evaluated in a titration assay to quantify the NAb level and will be reported as titer.

Definition of ADA Baseline

Baseline for ADA should be the last measurement prior to receiving the very first rozanolixizumab (RLZ) infusion in either MG0004 or the feeder study MG0003. Specifically, baseline for ADA is defined as:

- MG0003 ADA baseline if participants randomized to RLZ groups in MG0003 (note: MG0003 post-baseline ADA samples will not be considered for the ADA participant status in MG0004);
- MG0004 ADA baseline if participants randomized to placebo in MG0003.

If the ADA sample status for the visit prior to the first dose of RLZ is missing, the last non-missing sample will be used.

ADA/NAb Participant Status

The ADA participant status will be classified on study participant and group level as outlined below (Shankar et al. 2014; Rup et al, 2015). A description of how study participants will be categorized for the immunogenicity assessment is provided in

Table 10-1.

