10.3.2 ADA summaries

The following outputs will be presented on the SS.

Tables:

- Number and percentage of participants with ADA (positive, negative, inconclusive, missing) and NAb (positive, negative, missing) sample status at the time of each visit will be summarized by first dose received and RLZ total. Denominator is the number of study participants having a non-missing result at that visit.
- Number and percentage of participants in each of the individual and combined ADA participant status categories presented in [Table 10-1](#) will be summarized by first dose received and RLZ total at each scheduled visit and EOS visit. The table will be repeated by prior treatment in MG0003 (RLZ total or placebo) up to Week 9.

- Total prevalence of pre-existing ADA and NAb, defined as number and percentage of participants having an ADA positive sample status at baseline, with the denominator being the total number of study participants having an evaluable sample result at baseline. Missing samples will not be included in the denominator. The table will be repeated by prior treatment in MG0003 (RLZ or placebo). The same will be repeated for NAb.
- The first occurrence of treatment-emergent ADA positivity: cumulative number and percentage of TE-ADA positive participants (category 7) who are ADA positive for the first time at each visit. The table will be repeated by prior treatment in MG0003 (RLZ or placebo).
- Summary table of mean maximum percentage CFB in total IgG and mean CFB in MG-ADL, summarized by ADA participant categories 1, 2, 9, 10, 11 and 12 for the corresponding time period of interest and by treatment group and RLZ total [REDACTED].
- Overall summary table of TEAEs at Week 9 and EOS summarized by ADA participant categories 1, 2, 7 and 8 for the corresponding time period of interest.
- Summary of incidence of TEAE at Week 9 and EOS by ADA participant category 1, 2, 7 and 8 for the corresponding time period of interest.
- Summary table of AEOF hypersensitivity reactions, anaphylactic reactions and infusion reactions at Week 9 and EOS by ADA participant category 1, 2, 7 and 8 for the corresponding time period of interest.

Figures:

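### SAP Table 10-1 reports an ADA-positive participant with no evaluable NAb result as NAb negative, because categories 10 and 12 require only the absence of a positive result

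*SAP*

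**What the plan says.** At sample level, SAP section 10.3.1 gives NAb status three levels: "Neutralizing antibody (NAb) sample status (positive/negative/missing) will be determined for ADA positive samples". At participant level it gives two: "Both TE-ADA positive and non-TE-ADA positive participants will be further classified as NAb negative or NAb positive". Table 10-1 then sets the rules. Categories 9 and 11 (NAb positive) need at least one NAb-positive sample. Category 10 (NAb negative) reads "Includes study participants who are treatment emergent positive (category 7) and have no NAb positive samples", and category 12 reads "Includes study participants who are non-treatment emergent positive (category 8) and have no NAb positive samples".

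ADA status is handled differently. In Table 10-1 a participant is Inconclusive when "some post-Baseline samples are missing or inconclusive, while other post-Baseline samples are ADA negative".

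Entry to the immunogenicity analysis depends on ADA samples only. SAP section 10.3 admits "all study participants who have an evaluable pretreatment (baseline) sample (negative or positive ADA sample status), and at least 1 evaluable post-baseline value".

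The two documents differ on how many samples go to the NAb assay. SAP section 10.3 says that every sample confirmed positive in the binding assay will be tested. Protocol section 9.3.3.3 qualifies the ADA-positive samples in a parenthesis: "or subset of) further characterization for neutralizing ADA potential in vitro will be performed".

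**The concern.** Absence of a positive result is not a negative result. A participant with one ADA-positive sample and no NAb result has unknown NAb status, yet Table 10-1 offers only NAb positive or NAb negative and the wording selects negative. The ADA rule in the same table sends missing samples to a category of their own.

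At stake are the displays in SAP section 10.3.2 that use categories 9 to 12:

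- the participant-status table;
- the summary of maximum IgG change and MG-ADL change;
- the ADA-titer spaghetti and box plots;
- the MG-ADL time-course plot;
- the IgG spaghetti plots.

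These are among the planned looks at whether neutralising antibodies go with a weaker effect. Participants of unknown status in the NAb-negative group inflate its count and, if some are truly NAb positive, pull the two groups together.

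**Working it through.** The documents give no figure on this point, so there is nothing to reproduce. The check is one of logic, followed by an illustration of size.

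**Step 1: apply the rule to every pattern.** Each ADA-positive sample is NAb positive, negative or missing. Any positive sample gives NAb positive; otherwise the participant is NAb negative.

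| ADA-positive samples | Possible patterns | Patterns with a missing result, labelled NAb negative | Of these, all missing |
|---|---|---|---|
| 1 | 3 | 1 | 1 |
| 2 | 9 | 3 | 1 |
| 3 | 27 | 7 | 1 |

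The all-missing pattern is labelled NAb negative whatever the number of samples.

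**Step 2: look for a rule that overrides this.**
- The evaluability rule in SAP 10.3 concerns ADA results only, so it removes nobody for lacking a NAb result.
- The rule "Denominator is the number of study participants having a non-missing result at that visit" belongs to the by-visit sample-status table. The baseline prevalence table also leaves missing samples out. Neither rule is attached to the participant-category table, for which no denominator is stated.
- The general observed-data rule in SAP 3.1 does not help, because Table 10-1 has already given these participants a non-missing category.

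Nothing overrides it.

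**Step 3: can one missing result leave a participant with none?** Yes. Categories are derived cumulatively from Week 5. Post-Baseline ADA samples are scheduled at Weeks 5, 9, 21, 33, 45, 52 and 60, so a treatment-induced participant has at most one scheduled ADA-positive sample at Week 5 and two at Week 9. A treatment-reduced participant (category 5) is ADA positive at Baseline only, so a single sample settles the NAb label.

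**Step 4: size, under assumptions.** Among ADA-positive participants, let p be the true NAb-positive share and m the share with no NAb result, missing at random. Both are assumed. Then:
- share labelled NAb negative = 1 − p(1 − m);
- share with a real negative result = (1 − p)(1 − m);
- difference = m, the participants of unknown status;
- unknown share of the NAb-negative group = m / (1 − p(1 − m));
- true NAb positives in that group, f = mp / (1 − p(1 − m)).

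Example, p = 40% and m = 10%: labelled negative 1 − 0.36 = 64%; real negatives 0.6 × 0.9 = 54%; unknown share 0.10/0.64 = 15.6%; f = 0.04/0.64 = 6.3%.

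| p | m | Labelled NAb negative | Real negative result | Unknown share of group | True NAb positives in group (f) |
|---|---|---|---|---|---|
| 20% | 5% | 81% | 76% | 6.2% | 1.2% |
| 20% | 10% | 82% | 72% | 12.2% | 2.4% |
| 20% | 20% | 84% | 64% | 23.8% | 4.8% |
| 40% | 5% | 62% | 57% | 8.1% | 3.2% |
| 40% | 10% | 64% | 54% | 15.6% | 6.3% |
| 40% | 20% | 68% | 48% | 29.4% | 11.8% |
| 60% | 5% | 43% | 38% | 11.6% | 7.0% |
| 60% | 10% | 46% | 36% | 21.7% | 13.0% |
| 60% | 20% | 52% | 32% | 38.5% | 23.1% |

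A true mean difference D between NAb-positive and NAb-negative participants would appear as D(1 − f). With m = 0 every effect is zero.

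**Step 5: compare candidate rules.** Take two ADA-positive samples per participant, each NAb result missing independently with probability 0.2, a true NAb share of 20%, and both samples of a NAb-positive participant truly positive. NAb positive is 0.20 × (1 − 0.2²) = 0.192 under every rule.

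| Rule for NAb negative | NAb negative | NAb-positive share within categories 9–12 |
|---|---|---|
| Current: no positive sample | 1 − 0.192 = 0.808 | 0.192/1.000 = 19.2% |
| All samples negative | 0.80 × 0.8² = 0.512 | 0.192/0.704 = 27.3% |
| At least one negative, none positive | 0.80 × (1 − 0.2²) = 0.768 | 0.192/0.960 = 20.0% |

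Requiring every sample to be negative removes far more true negatives than true positives and overshoots. Requiring one evaluable negative recovers the assumed 20%.

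**The case against.** The strongest objection is that the problem may never arise. The SAP is the more detailed document on this analysis and intends a NAb test on every confirmed ADA-positive sample, so a missing result would be an incidental failure. That stands as a limit on size. It does not remove the gap, because the SAP itself lists missing as a NAb status and the protocol leaves room for testing a subset.

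A second objection also stands. A reader might infer that the wording of categories 10 and 12 lowers the number of NAb-positive participants found. It does not: that number is the count in categories 9 and 11, which the wording leaves alone. Any shortfall there comes from the missing assays. The reported percentage changes only if the denominator changes too.

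Third, missing NAb results are not hidden. The by-visit table shows them, the baseline prevalence table excludes them, the listing gives NAb sample status and titer for each participant and timepoint, and the scatter plots of MG-ADL and IgG change repeated by NAb titer do not use categories 9 to 12. The TEAE and hypersensitivity tables use categories 1, 2, 7 and 8. All this is correct and confines the point to the displays by categories 9 to 12.

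Finally, a participant with one negative and one missing result might be thought equally misclassified. That status is less certain, but it rests on an actual negative result, and step 5 shows that excluding such participants introduces a bias of its own.

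**Conclusion.** The point holds as a defect of definition. A participant with no evaluable NAb result is reported as NAb negative, and no other rule in the SAP prevents it. The NAb-negative count is too high by exactly the number of such participants, and they enter the NAb-negative group in the IgG, MG-ADL and ADA-titer displays.

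The size is unknown. It is zero with complete testing. In the assumed range (m from 5% to 20%, p from 20% to 60%, missing at random) the unknown share of the NAb-negative group runs from 6.2% to 38.5%, and a true group difference shrinks by 1.2% to 23.1%. The documents do not support stating as fact that NAb frequency is understated or that the groups are contaminated, since they give no rate of missing NAb results. All the affected analyses are descriptive, and no primary or secondary endpoint is touched. This is a minor point that is cheap to put right.

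**What to change.** In SAP Table 10-1 and section 10.3.1:

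1. Define categories 10 and 12 as at least one evaluable NAb-negative result and no NAb-positive sample up to the timepoint of interest.
2. Add a 'NAb not determined' row within categories 7 and 8 for participants with no evaluable NAb result. Show it in the participant-status table and keep these participants out of the displays by categories 9 to 12.
3. Base the NAb percentages on participants with at least one evaluable NAb result, and state that denominator.
4. Flag participants with partly missing NAb results in the listing; they keep the category that their available results give.
5. Amend the sentence in section 10.3.1 that allows only two NAb participant levels.

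The cost is a wording change, one extra row and possibly a few fewer participants in the NAb-negative groups. No new data are needed, and if no NAb result is missing the row is empty.
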